#### 2.8.1.2.1 Intracranial endpoints

**Overall intracranial response rate (OIRR):** OIRR is calculated based on response assessments in the brain for patients having measurable brain metastases at baseline. The OIRR is defined as the proportion of patients with a best overall confirmed response of CR or PR in the brain as assessed per modified RECIST 1.1.

OIRR will be estimated and the exact binomial 95% CI will be presented by study arm and for all patients. OIRR will also be summarized by prior radiotherapy to the brain (yes, no) and prior ALK inhibitor use (yes, no) and overall using the data from Arms 1 through 4. OIRR by the investigator and by BIRC will be summarized separately.

Same analysis on OIRR will be conducted for patients having evaluable (measurable or non-measurable) brain metastases at baseline.

**Intracranial disease control rate (IDCR) at 8 and 16 weeks and overall:** IDCR is calculated based on response assessments in the brain for patients having evaluable (measurable or non-measurable) brain metastases at baseline. In what follows, CR, PR and SD are possible responses only for patients with measurable brain metastases at baseline, while non-CR/non-PD is a possible response only for patients without measurable brain metastases at baseline.

- The IDCR at 8 and 16 weeks is defined as the proportion of patients with CR, PR, SD or non-CR/non-PD assessment in the brain at Week 8 and Week 16 intracranial tumor evaluations respectively, taking into consideration 4-week window for each assessment, i.e., assessment done between study day 29 and 85 (both inclusive) for week 8 and study day 86 and 141 (both inclusive) for week 16, as per modified RECIST 1.1. If there are multiple tumor assessments within the defined window, the following rules should be used hierarchically to select the overall response contributing to the xx-week IDCR rate:
  - 1) PD - If at least one tumor assessment with overall response of PD;
  - 2) Unknown - if all tumor assessment with overall responses of unknown;

3) CR/PR/SD - Overall response from the latest tumor assessment within the window

The assessment of SD too early or PD too late will be considered as Unknown and following the same rule specified in SAP [Section 2.7.1](#).

- IDCR overall is defined as the proportion of patients with a best overall response of CR, PR, SD or non-CR/non-PD in the brain, as assessed per modified RECIST 1.1.

IDCR will be estimated and the exact binomial 95% CI will be presented by study arm and for all patients. IDCR will also be summarized by prior radiotherapy to the brain (yes, no) and prior ALK inhibitor use (yes, no) and overall using the data from Arms 1 through 4. IDCR by the investigator and by BIRC will be summarized separately.

Same analysis on overall IDCR will be conducted for patients having measurable brain metastases at baseline.

**Time to intracranial tumor response (TTIR):** TTIR is defined as the time from the date of the first dose of ceritinib to the date of the first documented response (CR or PR) in the brain as assessed per modified RECIST 1.1 criteria for patients with measurable brain metastases at baseline.

TTIR will be summarized by frequency counts in time intervals and using descriptive statistics for patients with confirmed CR or PR.

These analyses of TTIR will be performed separately based on investigator and BIRC assessment.

Same analysis on TTIR will be conducted for patients having evaluable (measurable or non-measurable) brain metastases at baseline.

**Duration of intracranial response (DOIR):** Among patients with measurable brain metastases at baseline and a confirmed response (PR or CR) in the brain per Modified RECIST 1.1, DOIR is defined as the time from the first documented response (PR or CR) in the brain to the date of the first documented disease progression in the brain or death due to any cause. If a patient has not had an event, DOIR is censored at the date of last adequate tumor assessment.

The censoring and event date options to be considered for the main analysis are presented in [Table 2-2](#). Please note that the intracranial/extracranial/whole body tumor assessments apply to intracranial (DOIR), extracranial (DOER) and whole body (DOR and PFS) endpoints, respectively.

**Table 2-2 Outcome and event dates for DOIR, DOER, DOR and PFS analyses**

	Situation	Date	Outcome
A	No baseline intracranial/extracranial/ whole body assessment	Date of first dose of study drug a	Censored
B	Progression at or before next scheduled intracranial/extracranial/ whole body assessment	Date of progression	Progressed
C1	Progression or death after exactly one missing intracranial/extracranial/ whole body assessment	Date of progression (or death)	Progressed

	Situation	Date	Outcome
C2	Progression or death after two or more missing intracranial/extracranial/ whole body assessments	Date of last adequate intracranial/extracranial/ whole body assessment b	Censored
D	No progression	Date of last adequate intracranial/extracranial/ whole body assessment b	Censored
E	Treatment discontinuation due to 'Disease progression' without documented progression, i.e. clinical progression based on investigator claim	N/A	Information ignored. Outcome derived based on radiology data only.
F	New anticancer therapy given	Ignore the new anticancer therapy and follow situations above (ITT approach)	As per above situations

a The rare exception to this is if the patient dies no later than the time of the second scheduled assessment as defined in the protocol in which case this is a PFS event at the date of death

b After the last adequate tumor assessment. "Date of next scheduled assessment" is defined in [Section 14.2.25](#) of (Appendix 2) of the LDK378A2205 protocol.

DOIR will be described by study arm using Kaplan-Meier methods, including estimated median (in months) with 95% CI, 25th and 75th percentiles and Kaplan-Meier estimated probabilities with corresponding 95% CIs at pre-specified time points.

DOIR will also be summarized by prior radiotherapy to the brain (yes, no) and prior ALK inhibitor use (yes, no) using the data from Arms 1 through 4.

These analyses of DOIR will be performed separately based on investigator assessment and based on BIRC assessment.

Same analysis on DOIR will be conducted for patients having evaluable (measurable or non-measurable) brain metastases at baseline.

#### 2.8.1.2.2 Extracranial endpoints

**Overall extracranial response rate (OERR):** OERR is defined as the proportion of patients with a best overall confirmed response of CR or PR outside of the brain, as assessed per RECIST 1.1.

OERR will be estimated and the exact binomial 95% CI will be presented by study arm and for all patients. OERR will also be summarized by prior radiotherapy to the brain (yes, no) and prior ALK inhibitor use (yes, no) and overall using the data from Arms 1 through 4.

OERR by the investigator and by BIRC will be summarized separately.

#### **Extracranial disease control rate (EDCR) at 8 and 16 weeks and overall:**

- EDCR at 8 and 16 weeks is defined as the proportion of patients with CR, PR or SD outside of the brain at Week 8 and Week 16 extracranial tumor evaluations respectively, as assessed per RECIST 1.1. Same method will be used as for IDCR. See details in [Section 2.8.1.2.1](#).
- EDCR overall is defined as the proportion of patients with a best overall response of CR, PR or SD outside of the brain as assessed per RECIST 1.1.

EDCR will be estimated and the exact binomial 95% CI will be presented by study arm. EDCR will also be summarized by prior radiotherapy to the brain (yes, no) and prior ALK inhibitor use (yes, no) and overall using the data from Arms 1 through 4.

EDCR by the investigator and by BIRC will be summarized separately.

**Time to extracranial tumor response (TTER):** TTER is defined as the time from the date of the first dose of ceritinib to the date of the first documented response (CR or PR) outside of the brain as assessed per RECIST 1.1 criteria.

TTER will be summarized by frequency counts in time intervals and using descriptive statistics for patients with confirmed CR or PR.

These analyses of TTER will be performed separately based on investigator assessment and based on BIRC assessment.

**Duration of extracranial response (DOER):** Among patients with a confirmed response (PR or CR) outside of the brain per RECIST 1.1, DOER is defined as the time from the first documented response (PR or CR) outside of the brain to the date of the first documented disease progression outside of the brain or death due to any cause.

DOER will be described by study arm using Kaplan-Meier methods, including estimated median (in months) with 95% CI, 25th and 75th percentiles and Kaplan-Meier estimated probabilities with corresponding 95% CIs at pre-specified time points. .

Additionally, DOER will also be presented by prior radiotherapy to the brain (yes, no) and prior ALK inhibitor use (yes, no) and overall using the data from Arms 1 through 4.

These analyses of DOER will be performed separately based on investigator assessment and based on BIRC assessment.

#### 2.8.1.2.3 Whole body endpoints

**ORR by BIRC:** The evaluation of ORR will be repeated based on BIRC assessment by study arm and for all patients. Additionally, ORR by BIRC will also be presented by prior radiotherapy to the brain (yes, no) and prior ALK inhibitor use (yes, no) and overall using the data from Arms 1 through 4.

**DCR by BIRC:** The evaluation of DCR will be repeated based on BIRC assessment by study arm and for all patients. Additionally, DCR by BIRC will also be presented by prior radiotherapy to the brain (yes, no) and prior ALK inhibitor use (yes, no) and overall using the data from Arms 1 through 4.

**Time to tumor response (TTR):** TTR is defined as the time from the date of the first dose of ceritinib to the date of the first documented response (CR or PR) in the whole body as assessed per RECIST 1.1 criteria.

TTR will be summarized by frequency counts in time intervals and using descriptive statistics for patients with confirmed CR or PR.

These analyses of TTR will be performed separately based on investigator assessment and based on BIRC assessment.

**Duration of response (DOR):** Among patients with a confirmed response (PR or CR) in the whole body per RECIST 1.1, DOR is defined as the time from the first documented response (PR or CR) to the date of the first documented disease progression or death due to any cause.

DOR will be described by study arm and for all patients using Kaplan-Meier methods, including estimated median (in months) with 95% CI, 25th and 75th percentiles and Kaplan-Meier estimated probabilities with corresponding 95% CIs at pre-specified time points.

Additionally, DOR will also be presented by prior radiotherapy to the brain (yes, no) and prior ALK inhibitor use (yes, no) and overall using the data from Arms 1 through 4.

These analyses of DOR will be performed separately based on investigator assessment and based on BIRC assessment.

**Progression-free survival (PFS):** PFS is defined as the time from the date of the first dose of ceritinib to the date of the first radiologically documented disease progression in the whole body per RECIST 1.1 or death due to any cause. A patient who has not progressed or died at the date of the analysis cut-off will be censored at the time of the last adequate tumor evaluation performed on or before the cut-off date. By default, if disease progression or death for any reason is documented after one single missing tumor evaluation, the actual event date of disease progression/death will be used for the PFS event date. If disease progression or death for any reason is documented after two or more missing tumor evaluations, the PFS time of these patients will be censored at the date of the last adequate tumor evaluation without PD. Refer to [Table 2-2](#) for censoring and event date options and outcomes for PFS. See also [Section 4.6.1](#) describing the special case of a missing baseline tumor assessment.

PFS will be described by study arm using Kaplan-Meier methods, including estimated median (in months) with 95% CI, 25th and 75th percentiles and Kaplan-Meier estimated probabilities with corresponding 95% CIs at pre-specified time points. Censoring reasons will also be summarized.

These analyses will be performed separately based on investigator assessment and based on BIRC assessment. Additionally, PFS will also be presented by prior radiotherapy to the brain (yes, no) and prior ALK inhibitor use (yes, no) and overall using the data from Arms 1 through 4.

**Overall survival (OS):** OS time is defined as time from the date of first dose of ceritinib to the date of death due to any cause. OS time for patients who are alive by the date of the analysis cut-off or are lost to follow-up will be censored at the date of last contact.

OS will be described by study arm using Kaplan-Meier methods, including estimated median (in months) with 95% CI, 25th and 75th percentiles and Kaplan-Meier estimated probabilities with corresponding 95% CIs at pre-specified time points. Censoring reasons will also be summarized.

OS will be analyzed by study arm using the data from study arms 1 through 5. However, Kaplan-Meier curves of OS will not be produced for Arm 5 alone if the number of patients enrolled in this arm is  $\leq 10$ .

Additionally, OS will also be presented by prior radiotherapy to the brain (yes, no) and prior ALK inhibitor use (yes, no) and overall using the data from Arms 1 through 4.

### Duration of Follow-up

Follow-up in the study will be summarized using the following methods to provide a comprehensive assessment of follow-up for all patients.

Summary of duration between start date of study drug and cut-off date, and follow-up times for PFS/OS, are defined as follows:

- Duration between start date of study drug and data cut-off date = (Cut-off date – Start date of study drug + 1) / 30.4375 (months).
- Follow-up time = (Date of event or censoring – Start date of study drug + 1) / 30.4375 (months) regardless of censoring. Date of censoring is defined as the last adequate tumor assessment date for PFS or last contact date (when the patient is known as alive) for OS.

All summaries will be reported in months (see [Section 4.3](#)). The calculations for PFS will be based on investigator assessment and BIRC assessment.

### Exploratory endpoints

[REDACTED]

**OIRR by RANO:** OIRR by RANO will be estimated and the exact binomial 95% CI will be presented by study arm. OIRR by the investigator and by BIRC will be summarized separately.

**IDCR by RANO:** IDCR by RANO will be estimated and the exact binomial 95% CI will be presented by study arm. IDCR by the investigator and by BIRC will be summarized separately.

**TTIR by RANO:** Similar to TTIR by Modified RECIST 1.1, TTIR by RANO will be analyzed using frequency count and descriptive statistics by study arm.

These analyses of TTIR will be performed separately based on investigator assessment and based on BIRC assessment.

**DOIR by RANO:** Similar to DOIR by Modified RECIST 1.1, DOIR by RANO will be analyzed using Kaplan-Meier methods by study arm.

[REDACTED]

### 2.8.2 Safety

All safety analyses will be performed based on the Safety Set by study arm (Arms 1 to 5) and all patients.

### Observation periods for the analyses

CONFIDENTIAL - For Business Use Only

The overall observation period will be divided into three mutually exclusive segments:

- Pre-treatment period: from day of patient's informed consent to the day before first dose of study drug
- On-treatment period:
  - For discontinued patients, from day of first dose of study drug to 30 days after last dose of study drug
  - For ongoing patients, from day of first dose of study drug to the data cut-off date
- Post-treatment period: starting at day 31 after last dose of study drug

The safety summary tables will include only assessments collected during the on-treatment period.

For select items, shift tables or change from baseline summaries generated for laboratory, ECG, vital signs and change score (WHO PS) generation may use data from pre-treatment period for baseline calculations.

All data, regardless of observation period, will be listed and assessments collected during the pre-treatment and post-treatment period will be flagged in all the listings.

### **Adverse events (AEs)**

AEs will be coded using MedDRA using the latest version available prior to clinical database lock and will be graded using Common Terminology Criteria for Adverse Events (CTCAE) version 4.03. If CTCAE grading exists for an AE, grades 1, 2, 3, or 4 corresponding to the severity of mild, moderate, severe, and life-threatening, respectively, will be used. CTCAE grade 5 (death) will not be used in this study; rather, this information will be collected on the "End of Treatment Disposition", "End of Post Treatment Phase Disposition" or "Death" eCRF pages.

All AE summaries will be summarized (frequency counts and percentages) by primary system organ class (SOC) and/or preferred term (PT), maximum severity grades, and relation to study drug except where otherwise noted. A patient with multiple CTC grades for an AE will be summarized under the maximum CTC grade recorded for the event.

The following AE summaries will be produced:

- AEs regardless of study drug relationship
- AEs suspected to be study drug related
- All deaths, by primary SOC and PT
- On treatment deaths, by primary SOC and PT
- SAEs regardless of study drug relationship
- SAEs suspected to be study drug related
- AEs associated with discontinuation of study drug
- AEs requiring dose adjustment
- AEs requiring study drug interruption
- AEs requiring dose adjustment or study drug interruption
- AEs requiring significant additional therapy

CONFIDENTIAL - For Business Use Only

- AEs excluding SAEs

Per safety disclosure, two tables for on-treatment death/SAE and non-SAE will be summarized but not included in the CSR.

### **Adverse events of special interest**

Adverse events of special interest (AESIs) are defined as AEs within the following categories/groupings of preferred terms:

- Hepatotoxicity
- Interstitial lung disease/pneumonitis
- QTc prolongation
- Hyperglycemia
- Bradycardia
- GI toxicity (nausea, diarrhea, and vomiting)
- Pancreatitis

AESIs are defined at the project level and may be updated based on emergent data to reflect new AESIs at the time of analysis. The AESIs listed above will be identified based on a list of preferred terms. The final list of preferred terms is available in the electronic case retrieval strategy and will be presented in a separate annex of the document. These AESIs will be summarized for each grouping, by preferred term, as follows:

- All AESIs
- CTC grade 3/4 AESIs
- AESIs suspected to be study drug related
- CTC grade 3/4 AESIs suspected to be drug related
- Serious AESIs
- AESI leading to study drug discontinuation
- AESIs requiring dose adjustment or study drug interruption
- AESIs requiring dose adjustment
- AESIs requiring study drug interruption

### **Laboratory data**

For laboratory data assessments, data from all sources (central and local laboratories) will be combined. The summaries will include all laboratory assessments collected in the on-treatment period. All laboratory assessments will be listed and those collected prior to first dose of study drug or later than 30 days after study drug discontinuation will be flagged in the listings.

Laboratory data will be classified (by Novartis Oncology Statistical Programming) into CTC grades according to the NCI CTCAE v4.03. For all reports, CTC grade is always obtained on the converted measurement in SI unit. Grade 5 will not be used. The CTC grade 0 will be assigned as below in different scenarios:

1. For laboratory parameters defined by criteria based on normal range only, a severity grade of 0 will be assigned when the value is within normal limits.
2. For laboratory, parameters whose grade is defined by criteria based on normal range and absolute values (e.g. platelet count decrease). A severity grade of 0 will be assigned when the value is within normal limits.
3. For laboratory parameters whose grade is defined by criteria based on normal range and the change from baseline value, with no other associated clinical criteria such as concomitant medication (e.g. creatinine increased) the following will be applied. For the baseline grading and for the grading of post-baseline laboratory values with missing baseline grading, the grade will be derived using the criteria based only on the normal range as per CTCAE v4.03. A severity grade of 0 will be assigned when the post-baseline value is  $\leq$  ULN (for hyper) or  $\geq$  LLN (for hypo).

Parameters for which a grading does not exist will be classified into low/normal/high group by means of laboratory normal ranges.

The following summaries will be produced for the hematology and biochemistry laboratory data (by laboratory parameter):

- Shift tables using CTC grades to compare baseline to the worst post-baseline value for laboratory parameters with CTC grades
- Shift tables using low, normal, high (as well as low and high combined) classifications to compare baseline to the worst post-baseline value for laboratory parameters where CTC grades are not defined.

The following lab parameters will be summarized:

- Hematology: absolute lymphocytes, absolute neutrophils, hemoglobin (anemia), WBC, platelet counts, absolute basophils, absolute eosinophils, absolute monocytes, RBC.
- Biochemistry: alkaline phosphatase (ALP), SGPT (ALT), SGOT (AST), total bilirubin, amylase, lipase, potassium (hyper and hypo), sodium (hyper and hypo), creatinine, glucose (hyper and hypo), phosphate, albumin, calcium (corrected for albumin), magnesium, creatinine clearance, direct bilirubin, blood urea nitrogen (BUN) or urea, GGT.
- For bi-directional parameters, both hyper and hypo summaries will be presented.

All hematology and biochemistry will be listed as per protocol. Further, following laboratory parameters will be presented in listings and will not be summarized:

- Coagulation: INR, pro-thrombin time (PT) or Quick Test.

Other laboratory parameters collected and not described above may be summarized if clinically indicated.

The following listings will be produced for the laboratory data for all laboratory parameters where CTC grades are defined:

- Listing of patients with laboratory abnormalities of CTC grade 3 or 4.
- Listing of all laboratory data with values flagged to show the corresponding CTC grades and the classifications relative to the laboratory reference ranges.

Liver function tests (LFTs) of interest for ceritinib are total bilirubin (TBILI), ALT, AST and ALP. In what follows, AT refers to ALT or AST values. LFTs will be summarized as follows:

- Shift tables of baseline vs. worst post-baseline on-treatment values for the categories:
  - $TBILI \leq 2xULN$ ,  $TBILI > 2xULN$  and missing TBILI
  - $ALT \leq 3xULN$ ,  $ALT > 3xULN$  and missing ALT
  - $AST \leq 3xULN$ ,  $AST > 3xULN$  and missing AST
  - $ALP < 2xULN$ ,  $ALP \geq 2xULN$  and missing ALP
- Frequency counts and percentages of patients with worst post-baseline on-treatment values in the categories:
  - $ALT > 3xULN$ ,  $ALT > 5xULN$ ,  $ALT > 10xULN$ ,  $ALT > 20xULN$
  - $AST > 3xULN$ ,  $AST > 5xULN$ ,  $AST > 10xULN$ ,  $AST > 20xULN$
  - $AT > 3xULN$ ,  $AT > 5xULN$ ,  $AT > 10xULN$ ,  $AT > 20xULN$
  - $TBILI > 2xULN$
  - Concurrent  $ALT > 3xULN$  and  $TBILI > 2xULN$
  - Concurrent  $AST > 3xULN$  and  $TBILI > 2xULN$
  - Concurrent  $AT > 3xULN$  and  $TBILI > 2xULN$
  - Concurrent  $AT > 3xULN$  and  $TBILI > 2xULN$  and  $ALP < 2xULN$
  - Concurrent  $AT > 3xULN$  and  $TBILI > 2xULN$  and  $ALP \geq 2xULN$

Concurrent measurements are those occurring on the same date.

In addition, a listing of all TBILI, ALT, AST and ALP values for patients with a post-baseline  $TBILI > 2xULN$ ,  $ALT > 3xULN$  or  $AST > 3xULN$  will be provided.

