Grade 4 (PLT < $25 \times 10^9/L$)	Mandatory: Omit dose until resolved to \leq Grade 2, then \downarrow 1 dose level
HEPATIC	
Alkaline phosphatase and/or Gamma-glutamyl transpeptidase (GGT)	
Isolated elevations of any grade	Recommendation: Maintain dose level
Total Bilirubin** (for patients with Gilbert Syndrome these dose modifications apply to changes in direct [conjugated] bilirubin only)	
Grade 1 ($> ULN$ and $\leq 1.5 \times ULN$)	Recommendation: Maintain dose level with liver function test (LFTs)*** monitored as per protocol
Grade 2 (> 1.5 and $\leq 3.0 \times ULN$) with ALT or AST $\leq 3.0 \times ULN$	Mandatory: Omit dose until resolved to \leq Grade 1, then it is recommended: If resolved in ≤ 7 days, to maintain dose level If resolved in > 7 days, to \downarrow 1 dose level

[figure not shown]
Worst toxicity (CTCAE 4.03 Grade)*	Dose Modifications for ceritinib
Grade 3 (> 3.0 and ≤ 10.0 x ULN) with ALT or AST ≤ 3.0 x ULN	Mandatory: Omit dose until resolved to ≤ Grade 1, then it is recommended: If resolved in ≤ 7 days, to ↓ 1 dose level If resolved in > 7 days, to discontinue patient from ceritinib
Grade 4 (> 10.0 x ULN)	Mandatory: Permanently discontinue patient from ceritinib
AST or ALT	
Grade 1 (> ULN and ≤ 3.0 x ULN)	Recommendation: Maintain dose level with LFTs*** monitored per protocol
Grade 2 (> 3.0 and ≤ 5.0 x ULN) without total bilirubin elevation to > 2.0 x ULN	Recommendation: Maintain dose level with LFTs*** monitored per protocol
Grade 3 (> 5.0 and ≤ 20.0 x ULN) without total bilirubin elevation to > 2.0 x ULN	Mandatory: Omit dose until resolved to ≤ Grade 1, then ↓ 1 dose level
Grade 4 (> 20.0 x ULN) without total bilirubin elevation to > 2.0 x ULN	Mandatory: Omit dose until resolved to ≤ Grade 1, then ↓ 1 dose level
AST or ALT and concurrent Total bilirubin	
AST or ALT > 3.0 x ULN with total bilirubin > 2.0 x ULN in the absence of cholestasis or hemolysis	Mandatory: Permanently discontinue patient from ceritinib Refer to Section 6.3.4.2 for additional follow-up
RENAL	
Serum creatinine	
Grade 1 (>1 and ≤1.5 x baseline; >ULN and ≤ 1.5 x ULN)	Recommendation: Maintain dose level
Grade 2 (> 1.5 and ≤ 3 x baseline; >1.5 and ≤3.0 x ULN)	Recommendation: Omit dose until resolved to ≤ Grade 1, then it is recommended: If resolved in ≤ 7 days, then maintain dose level If resolved in > 7 days, then ↓ 1 dose level
Grade 3 (>3.0 x baseline; > 3.0 and ≤ 6.0 x ULN)	Mandatory: Omit dose until resolved to ≤ Grade 1, then ↓ 1 dose level

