6.3.4.3 Guidelines for the follow-up of laboratory renal abnormalities

In case of any occurrence of serum creatinine grade 2, tests must be performed weekly (or more frequently if clinically indicated) until the event resolves to \leq grade 1. Subsequent monitoring must be performed every 4 weeks.

In case of any occurrence of serum creatinine \geq grade 3, tests must be performed twice weekly (or more frequently if clinically indicated) until the event resolves to \leq grade 1. Subsequent monitoring must be performed every 4 weeks. See [Table 6-4](#).

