10.5.3.3 Laboratory abnormalities

For laboratory tests covered by the CTCAE version 4.03, the study's biostatistical and reporting team will grade laboratory data accordingly. For laboratory tests covered by CTCAE, a Grade 0 will be assigned for all non-missing values not graded as 1 or higher (In the unlikely case when a local laboratory normal range overlaps into the higher (i.e. non-zero) CTC grade, the laboratory value will still be taken as within normal limits and assigned a CTC grade of zero.). Grade 5 will not be used.

For laboratory tests where grades are not defined by CTCAE, results will be graded by the low/normal/high classifications based on laboratory normal ranges.

The following by-treatment summaries will be generated separately for hematology, biochemistry and urinary laboratory tests:

- shift tables using CTCAE grades to compare baseline to the worst on-treatment value
- for laboratory tests where CTCAE grades are not defined, shift tables using the low/normal/high/(low and high)

Listing of all laboratory data with values flagged to show the corresponding CTCAE grades and the classifications relative to the laboratory normal ranges will be generated.

A separate listing will display notable laboratory abnormalities (i.e., newly occurring CTCAE grade 3 or 4 laboratory toxicities).

[figure not shown]
[figure not shown]

[figure not shown]

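### Creatinine at or below ULN is graded 0 whatever its rise from baseline, so the shift table can under-grade rises that Protocol Table 6-3 calls grade 2

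*SAP*

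**What the plan says.** SAP 2.8.2, Laboratory data, item 3 covers parameters graded on normal range and change from baseline, "with no other associated clinical criteria such as concomitant medication (e.g. creatinine increased) the following will be applied". It allows range-only grading in two situations, the baseline value itself and post-baseline values without a baseline grade: there, "the grade will be derived using the criteria based only on the normal range as per CTCAE v4.03". Its last sentence is general: "A severity grade of 0 will be assigned when the post-baseline value is" at or below ULN for increases. These grades feed the baseline-to-worst shift tables and the grade 3 or 4 listing.

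Protocol Table 6-3 (Section 6.3.3), headed CTCAE 4.03, has for serum creatinine "Grade 2 (> 1.5 and ≤ 3 x baseline; >1.5 and ≤3.0 x ULN") and "Grade 3 (>3.0 x baseline; > 3.0 and ≤ 6.0 x ULN"). The grade 2 action is "Recommendation: Omit dose until resolved to ≤ Grade 1, then it is recommended"; the grade 3 action is labelled mandatory. Section 6.3.4.3 adds: "In case of any occurrence of serum creatinine grade 2, tests must be performed weekly".

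Protocol 10.5.3.3 says that for tests covered by CTCAE 4.03 the "biostatistical and reporting team will grade laboratory data accordingly". It reserves grade 0 for values not graded 1 or higher, with an exception for a local normal range that overlaps a non-zero grade, which it describes as unlikely.

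**The concern.** Item 3 limits range-only grading to baseline and missing-baseline values, which implies that the ratio to baseline counts otherwise. The grade 0 sentence then removes that ratio for every value within the normal range. Site actions and the report would follow two different gradings under one CTCAE version.

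At stake is the creatinine shift table. A rise that the protocol's own table calls grade 2 can be tabulated as grade 0. If the dose was held for it, the shift table will not match the AE and dosing tables. If nothing was done and the investigator did not judge it clinically significant, it need not be an adverse event, and the only trace is a line in the full laboratory listing, flagged grade 0. Renal toxicity is not among the adverse events of special interest in the SAP, so no dedicated table makes up for this. SAP Table 3-1 does not record the rule as a change from the protocol.

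**Working it through.** The plan states no figure to reproduce here. The check compares the two rules and then asks how often they could differ.

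**Inputs from the documents.** Table 6-3: grade 1 above 1 and up to 1.5 times baseline, or above ULN and up to 1.5 times ULN; grade 2 above 1.5 and up to 3 times either; grade 3 above 3 times baseline, or above 3 and up to 6 times ULN; grade 4 above 6 times ULN. SAP item 3: grade 0 at or below ULN. Inclusion criterion 7a caps creatinine and sets no lower limit.

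**Assumed inputs.** ULN of 1.0, 1.2 or 1.4 mg/dL, and a baseline distribution; the documents give neither.

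**1. Where the rules differ.** With baseline B and value V, a grade 2 is masked when 1.5B < V ≤ ULN. That is possible only if B < ULN/1.5:
- ULN 1.0: 1.0/1.5 = 0.67 mg/dL
- ULN 1.2: 1.2/1.5 = 0.80 mg/dL
- ULN 1.4: 1.4/1.5 = 0.93 mg/dL

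A grade 3 is masked when 3B < V ≤ ULN, so B < ULN/3: 0.33, 0.40 and 0.47 mg/dL. Grade 4 needs V above 6 times ULN and cannot be masked.

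**2. Worked values at ULN 1.2 mg/dL.**

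| Baseline | Value | × baseline | × ULN | Table 6-3 | SAP item 3 |
|---|---|---|---|---|---|
| 0.50 | 0.80 | 1.60 | 0.67 | 2 | 0 |
| 0.60 | 1.00 | 1.67 | 0.83 | 2 | 0 |
| 0.60 | 1.30 | 2.17 | 1.08 | 2 | 2 |
| 0.80 | 1.00 | 1.25 | 0.83 | 1 | 0 |
| 0.38 | 1.18 | 3.11 | 0.98 | 3 | 0 |

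The SAP rule jumps at ULN. From baseline 0.60, a value of 1.20 (2.00 times) is grade 0 and 1.21 (2.02 times) is grade 2.

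**3. Share masked, given a rise.** Take a rise to 1.8 times baseline, a grade 2 in Table 6-3. It is masked if 1.8B ≤ ULN. With B log-normal, median m, and σ = √ln(1 + CV²), the share is Φ(ln(ULN/(1.8m))/σ). For ULN 1.2, m = 0.75 and CV 20%: ln(0.667/0.75) = −0.118, σ = 0.198, ratio −0.595, share 28%. Over CV 20% to 30%:

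| ULN | m = 0.75 | m = 0.90 |
|---|---|---|
| 1.0 | 6–15% | 1–5% |
| 1.2 | 28–34% | 6–15% |
| 1.4 | 55–57% | 23–31% |

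Setting σ equal to the CV moves the 34% to 35%. All of these are conditional on the 1.8-fold rise having happened.

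**4. Grade 3.** Under the same model with m = 0.75, the share of patients with baseline below ULN/3 is 0.1%, 0.5% and 1.6% at ULN 1.2 (CV 20%, 25%, 30%), and 0.8% to 5.3% at ULN 1.4. A masked grade 3 also needs a rise of more than threefold that stays within the normal range.

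**The case against.** **The rule is a deliberate convention.** All three items in that SAP list give grade 0 to values within normal limits, and Protocol 10.5.3.3 takes a similar line for overlapping local ranges. An unrestricted baseline criterion would make any value above baseline grade 1, so ordinary fluctuation would count. This stands as a reason to keep grade 0 for small in-range rises. It does not cover rises above 1.5 times baseline: the protocol exception concerns range limits, not change from baseline.

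**The information is not lost.** Protocol 8.1.1 and 8.1.2.1 make a laboratory abnormality that requires a change or hold of study drug an adverse event. The SAP tabulates AEs by maximum grade and by dose adjustment or interruption, summarises creatinine clearance and lists all laboratory values. This stands for rises that were acted on. It does not reach rises that were not, and dose omission at grade 2 is only a recommendation.

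**The semicolon in Table 6-3 might mean that both conditions are needed.** The conflict would then vanish. But a value at 1.6 times baseline and 1.2 times ULN would fit no grade, and SAP item 3 itself uses the range criterion alone, so reading it as alternatives is sounder.

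**Stronger readings.** A reader might infer that the grade 3 or 4 listing materially understates renal toxicity. The documents do not support that: a masked grade 3 needs a baseline below one third of ULN, and Protocol Table 1-1 shows no grade 3 or 4 creatinine events among 255 patients, beside 39 (15.3%) of any grade. A reader might also take 28% to 35% as a misclassification rate. It is a conditional share at one ULN and one median, and it changes widely with both.

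**Conclusion.** The point holds for grade 2. As written, SAP item 3 gives grade 0 to creatinine values at or below ULN that Table 6-3 grades 2, whenever baseline is below ULN/1.5 and the rise exceeds 1.5 times baseline. The creatinine shift table will under-grade some rises and can disagree with the AE and dosing tables. Masked grade 3 is possible but should be rare.

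No expected number of patients can be derived. Neither the frequency of such rises nor the distribution of baseline creatinine is given, and the conditional share runs from about 1% to 35% at ULNs of 1.0 to 1.2 mg/dL, reaching 57% at 1.4 with the lower median. The conclusion rests on reading the two limbs of Table 6-3 as alternatives and on the grade 0 sentence applying when baseline is available; if the sponsor meant it only for missing baselines, the text does not say so. No efficacy endpoint is affected, and no view is taken on which dose rule is right.

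**What to change.** Reconcile SAP item 3 with Table 6-3:

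- When baseline is available, restrict grade 0 for values at or below ULN to those not above 1.5 times baseline, and apply the grade 2 and 3 baseline criteria otherwise. Use the same grade in the shift table and the grade 3 or 4 listing.
- Footnote that values at or below ULN and up to 1.5 times baseline stay at grade 0 by convention, although Table 6-3 calls those above baseline grade 1.
- Record the rule in SAP Table 3-1.

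If the sponsor keeps the present rule, footnote it and add counts of patients with creatinine above 1.5 and above 3 times baseline.

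The cost is one SAP sentence, a footnote, a row in Table 3-1 and a change to one grading macro, or one short extra table. No new data are needed. Some patients may move from grade 0 to grade 2 in the creatinine shift table.
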